## ***8.2 Schedule of Data Entry***

1. Within 48 hrs of randomization: Demographic and admission data
2. Within 72 hrs of discharge: Procedural data, imaging data, clinical course data, and discharge data
3. Within 72 hrs of follow-up imaging (angiogram or MRA): 3-6 month angiogram or MRA and 3-6 month clinical status
4. Within 72 hrs of follow-up angiogram or MRA: 12-18 month follow-up angiogram, 12-18 month clinical status
5. Notification for serious, unexpected complications (procedural or otherwise) or deaths will be available for review by the DSMB within 15 days of the receipt

## ***8.3 Data Monitoring***

Routine data monitoring will occur to ensure data validity. For the first two subjects at each site, source documentation and target data points will be reviewed for accuracy and at least 20% of the source documentation and target data points will be monitored thereafter. Study data monitoring will be conducted remotely through the uploading of identifiable data via a secure web-based electronic data capture system. Monitoring may also occur in person, or by telephone, on an as needed basis. All monitoring activities will be tracked and stored in the web-based data capture system overseen by Vanderbilt University Medical Center.

## **9. Statistical Methods**

### ***9.1 Sample Size Estimate and Power of the Study***

Based upon a presumed absolute improvement in recanalization rate (defined as an increase in Raymond Scale from immediate to 12-18 month follow-up, as determined by the core laboratory analysis) of 9% (73% recanalization rate for non-Eighteen versus 82% for Eighteen) with an Alpha 0.05 and Power = 80, 325 patients would be required for each arm (at least 650 total patients).

## **10. Committees and Centers**

### ***10.1 Trial Steering Committee (TSC)***

The TSC will meet as needed but no less than semi-annually. Its main function will be to monitor and supervise the progress of the randomized trial. It will consider recommendations of the DSMB and relevant ethics committees. At regular intervals it will review relevant information arising from other sources and make decisions regarding trial presentation/publication of interim and final results.

### ***10.2 Trial Coordinating Center***

The Trial Coordinating Center will be responsible for the daily running of the trial and will be located at the Vanderbilt University Medical Center. Duties include: facilitating site start-up, protocol and eDC training, facilitating timely completion of project milestones, oversight of regulatory affairs and compliance, data management, ensuring data integrity, site monitoring management, and safety oversight.

### ***10.3 Center and Investigator Requirements***

1. Neurosurgical care centers with case volume of aneurysm treatment greater than 60 cases per year.
2. Experienced endovascular treatment centers and operators.
3. High quality digital subtraction angiography equipment, preferably with 3D and biplane capability.
4. Willing to adhere to protocol and only use the required coils in enrolled patients and not polymer-enhanced, bioactive or other coils in same patient.

5. Local ethics approval and multi-center ethics approval in process by coordinating center.

## 11. Publication Policy

The TSC will be responsible for organizing a writing committee once trial recruitment is completed. That committee will formulate timelines for presentation/publication of results on behalf of the TSC and advise on appropriate journals for submission.

## 12. Financial and Insurance Matters

As Eighteen platinum coils are FDA-approved and used at many institutions and no randomized data exists regarding the use of framing coils in aneurysm embolization, both the use or non-use of these coils in aneurysm embolization are considered Standard of Care and shall be covered by the patient (whether insurance or self-pay).

**MODIFCATION HISTORY**

Version Number	Date of Document Version	Significant Changes from Previous Authorized Version
1.0	3/27/2024	Not applicable – first version

**ABBREVIATIONS AND DEFINITIONS**

ACT	Activated Clotting Time
AE	Adverse event
CI	Confidence Interval
DSMB	Data and Safety Monitoring Board
FEAT	Framing Eighteen coils in cerebral Aneurysms Trial
ISAT	International Subarachnoid Aneurysm Trial
ITT	Intent-to-treat
ICH	Intracerebral hemorrhage
IVH	Intraventricular hemorrhage
mRS	Modified Rankin Scale
NIHSS	National Institutes of Health Stroke Scale
SAE	Serious adverse event
SAP	Statistical Analytical Plan
WFNS	World Federation of Neurosurgical Societies

**PURPOSE OF STATISTICAL ANALYTICAL PLAN (SAP)**

The purpose of this SAP is to outline the planned analyses to be completed for the FEAT trial. The analyses identified in this SAP will be included in abstracts and manuscripts reporting the results of the trial. Exploratory analyses not necessarily identified in this SAP may also be performed. Any post hoc, or unplanned, analyses not explicitly identified in this SAP will be clearly identified as such in any published papers from this study. This SAP may be updated in response to additional developments, either within or outside the trial. All revisions will be made prior to the data lock and the primary analysis.

## 1. INTRODUCTION

Since the results of the International Subarachnoid Aneurysm Trial (ISAT) were published in 2002, the treatment of intracranial aneurysms has increasingly shifted from surgical to endovascular management. ISAT demonstrated improved mortality and dependency rates at 1-year in patients that underwent endovascular coil embolization compared to patients that underwent clipping (Molyneux 2002). However, longer-term follow-up revealed a higher incidence of late re-bleeding and recurrence among aneurysms treated via embolization compared to clipping (Molyneux 2005). The incidence of recurrence has been consistent in the literature, with an estimated angiographic recurrence rate of approximately 10-20% (although as high as 33% in one study); however, the re-bleed rate has consistently been low (Byrne 1999, Hayakawa 2000, Cognard 1999, Ng 2002, Thornton 2002, Raymond 2003). As such, many institutions have shifted towards endovascular management with follow-up to detect recurrence.

A major focus over the past decade has been improving aneurysm occlusion and recurrence rates through modification of techniques, devices, and embolic materials. Studies suggest that larger diameter platinum coils may be more stable during and after endovascular aneurysm coil embolization, and that smaller diameter framing coils may have a higher propensity towards recanalization. As such this study aims to evaluate the safety and effectiveness of larger diameter versus smaller diameter coils in patients undergoing endovascular treatment for a mid-sized aneurysm.

## 2. STUDY OBJECTIVES

### 2.1 Primary Objective

The primary objective of this trial is to evaluate the effectiveness and safety of larger diameter (0.014-0.0155 inch) coils compared to smaller diameter (<0.014 inch) coils for the endovascular treatment of mid-size aneurysms.

## 3. STUDY OVERVIEW

### 3.1 Study Design

This is a prospective, multi-center, randomized, clinical trial in patients with mid-size aneurysm. Patients will be randomized (1:1) to receive either larger diameter coils or smaller diameter coils.

#### 3.1.1 Study Duration and Time Points

All patients will be followed for 12 to 18 months post-procedure. Endpoints will be measured at discharge from the index procedure, 3 to 6 months post-procedure, and 12 to 18 months post-procedure. The 3 to 6 month visit and 12 to 18 month visit align with standard of care visits.

#### 3.1.2 Randomization and Masking

Patients will be randomly assigned in a 1:1 allocation to receive either larger or smaller coils. Patient randomization will be stratified by clinical site, aneurysm status (recently ruptured versus not), and dome to neck ratio (wide neck versus not). Randomization will be performed centrally through a web-based data collection system that automates the delivery of the randomization assignments.

Investigators will not be blinded to treatment assignment due to the nature of the treatment intervention. Investigators will, however, be blinded to all data from other clinical sites. Clinical outcome assessments will be completed by certified research staff that are not part of the treatment team. All angiograms will be analyzed by a blinded angiogram core laboratory personnel who will be blinded to clinical outcomes. Trial oversight will be provided by an independent Data and Safety Monitoring Board (DSMB).

#### 4. ANALYSIS POPULATIONS

Three populations will be used for all summaries and analyses.

##### **Screened Population**

The screened population will consist of all screened patients. A screened patient is defined as a subject referred to, or identified at, a clinical site for consideration of entry into the study.

##### **Intent-to-Treat (ITT) Population**

The ITT population will consist of all randomized subjects grouped by their assignment at randomization regardless of whether or not they actually received the treatment to which they were assigned. This sample will be used for summaries and analyses of the primary endpoint and the secondary clinical endpoints. The ITT population will be used for all effectiveness analyses and descriptions of patient and baseline characteristics.

##### **Safety Population**

The safety population will consist of all randomized subjects who initiate endovascular coiling, grouped by their assignment at randomization regardless of whether or not they actually received the coil size to which they were assigned. The safety population will therefore be identical to the ITT population if all randomized patients receive attempted vascular coiling. The safety population will be used to present safety summaries and for the analysis of safety data.

#### 5. STUDY ENDPOINTS

##### **5.1 Primary Endpoint**

The primary endpoint is angiographic occlusion at 12 to 18 months post-randomization as measured by a Raymond score of 1 or 2 (adequate occlusion). Patients' angiograms for the 3 to 6 month visit, the 12 to 18 month visit, and any clinically driven angiogram taken prior to 18 months post-randomization or study exit will be considered for angiographic occlusion. If any of these angiograms show inadequate angiographic occlusion (Raymond score >2), the patient will be considered to have inadequate occlusion at the 12 to 18 month visit and be considered a treatment failure.

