## **3. Objectives**

### **3.1 Primary Outcome**

Occlusion rate: Angiographic occlusion, improvement or no change in the post-coiling appearance of the aneurysm as judged by an independent core lab on follow-up angiography at 12-18 months after endovascular embolization.

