#### 5.1.2 Research methods

1. Investigators should only randomize patients if they believe they can actually treat the patient equally safely and effectively regardless of the presence or absence of a 0.014-0.0155” platinum coil(s).

2. As far as possible, the intention is to exclusively use 0.014-0.0155” bare platinum coils for the initial coil in the Eighteen coil treatment arm and for as many subsequent coils as safe and appropriate, as determined by the treating physician. However, if for any reason a treating physician needs to forego placement of a 0.014-0.0155” coil or use a different coil for this purpose, the patient will remain in the study according to the intention to treat principle. Conversely, in patients assigned to the non-Eighteen coil treatment arm, no 0.014-0.0155” platinum coil is to be placed. However, if for any reason the treating physician determines he/she needs to place a 0.014-0.0155” bare platinum coil, the patient will remain in the study according to the intention to treat principle.

3. JPG’s of de-identified images will be uploaded for independent evaluation and stored in the study’s electronic database. These images will be reviewed by an independent, blinded core lab.

4. An electronic case report form (eCRF) will be completed at the end of the procedure. The procedural details collected for the eCRF will include findings of angiographic anatomy, size, location, neck size and dome-to-neck ratio .

5. At time of discharge, any adverse events will be recorded on the eCRF.

6. Data on any further aneurysm treatment or re-treatment of the study treated aneurysm will be collected during the study period.

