### 5.2.3 Re-hemorrhage/Re-treatment

- Incidence of re-hemorrhage through the end of study follow-up at the 12 to 18 month visit.
- Incidence of re-treatment of the aneurysm through the end of study follow-up at the 12 to 18 month visit.

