### 6.5.3 *Missing Primary Endpoint Data*

Patients without previous evidence of inadequate angiographic occlusion, either on the 3 to 6 month visit angiogram or on a clinically driven angiogram taken prior to study exit, that miss the 12 to 18 month angiogram, or whose 12 to 18 month angiogram is not readable by the core lab, will be missing the primary endpoint. Patients missing the primary endpoint who die prior to or during the 12 to 18 month visit window (up to 18 months post-randomization) and die with known cause of death related to their aneurysm or unknown cause of death will be considered treatment failures with inadequate occlusion. Patients missing the primary endpoint with a known cause of death unrelated to their aneurysm will be considered missing.

Patients with missing primary endpoint data will have their 12 to 18 month angiographic

occlusion status imputed via multiple imputation assuming that the data are missing at random. The imputation model will be stratified by randomization assignment and include age, sex, randomization strata for aneurysm status, randomization strata for wide neck status, aneurysm size, and angiographic occlusion status at the 3 to 6 month visit. Since this model includes a mixture of variables types (i.e. continuous and binary), a fully conditional specification method will be used (Berglund 2014).

The main feature of the imputation approach is the creation of a set of clinically reasonable imputations for angiographic occlusion for each patient with missing data. This will be accomplished using a set of repeated imputations created by predictive models based on the majority of participants with complete data. The imputation models will reflect uncertainty in the modeling process and inherent variability in patient outcomes, as reflected in the complete data. Thirty datasets will be imputed.

After the imputations are completed, all of the data (complete and imputed) will be combined and the analysis performed for each imputed-and-completed dataset. Rubin's method of multiple (i.e., repeated) imputation will be used to estimate treatment effect (Rubin 1986).

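### The SAP does not say how re-treatment before the 12-18 month reading enters the primary endpoint, so some re-treated aneurysms score as successes of the first treatment

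*Combined protocol and SAP*

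**What the plan says.** SAP 5.1 defines success as Raymond 1 or 2 at 12 to 18 months. It counts the 3-6 month scan and the 12-18 month scan, and adds that "any clinically driven angiogram taken prior to 18 months post-randomization or study exit will be considered for angiographic occlusion". The failure rule is: "If any of these angiograms show inadequate angiographic occlusion (Raymond score >2), the patient will be considered to have inadequate occlusion". A later, better scan does not reverse it.

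SAP 6.5.3 adds one failure that does not depend on imaging. Among patients missing the endpoint, those who "die with known cause of death related to their aneurysm or unknown cause of death will be considered treatment failures with inadequate occlusion". The missing-data rule covers "Patients without previous evidence of inadequate angiographic occlusion, either on the 3 to 6 month visit angiogram or on a clinically driven angiogram" who have no readable 12-18 month scan. Unless the death rule applies, their outcome is imputed within arm from age, sex, rupture stratum, neck stratum, aneurysm size and 3-6 month occlusion status.

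Re-treatment appears elsewhere. SAP 5.2.3 lists as a secondary endpoint "Incidence of re-treatment of the aneurysm through the end of study follow-up at the 12 to 18 month visit", and SAP 6.6.4 compares it between arms by the Fine and Gray method. Protocol 5.1.2 states: "Data on any further aneurysm treatment or re-treatment of the study treated aneurysm will be collected during the study period". The visit schedule in protocol 6.1 has a re-treatment row at both follow-up visits and at unscheduled visits.

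**The concern.** Protocol section 4 (the text on the three phases, under 4.2) puts the trial's question as whether larger framing coils make treatment more durable. If an aneurysm is coiled again and then looks occluded, the scan shows the result of the second treatment. SAP 5.1 already applies this logic in part, since occlusion after an earlier score above 2 cannot rescue the patient. It leaves out the patient who was re-treated without such a score on record.

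A second gap lies in the same rule. Clinically driven scans have a latest date but no earliest one, and the clock starts at randomization. A scan soon after coiling that shows only the immediate result can therefore fix a permanent failure.

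SAP 3.1.2 states that investigators are not blinded. They can influence who is re-treated and who gets an extra scan, so neither kind of misclassification need be equal between arms. Blinded core-lab reading does not remove this, because the lab grades only the scans that exist.

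**Working it through.** **Step 1. Apply SAP 5.1 and 6.5.3 to the possible patients.**

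| Course | Final scan | Scored as |
|---|---|---|
| Counted scan above Raymond 2, then re-treated | Raymond 1 | Failure |
| Re-treated for a Raymond 2 remnant | Raymond 1 or 2 | Success |
| Re-treated; preceding scan unreadable or missing | Raymond 1 or 2 | Success |
| Either of the last two courses | Raymond 3 | Failure |
| Either of those two courses | Missing, patient alive | Imputed, re-treatment not in the model |
| Raymond 3 on a clinically driven scan days after coiling, not re-treated | Raymond 1 | Failure |

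Rows 2, 3 and 5 are the re-treatment gap. Row 6 is the early-scan gap.

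**Step 2. Reproduce the plan's power.** Inputs from SAP 6.5.2: 73% and 82% success, 325 per arm, two-sided 0.05.

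Power = Φ[(d − 1.96·se0)/se1], where p̄ is the mean of the two rates, se0 = √(2p̄(1−p̄)/n) and se1 = √((p1(1−p1) + p2(1−p2))/n).

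With d = 0.09 and p̄ = 0.775, se0 = 0.5906/√325 = 0.03276 and se1 = 0.5871/√325 = 0.03257. Power = Φ(0.792) = 78.6%, which agrees with the stated approximately 80%. Exactly 80% needs 337 per arm.

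**Step 3. Assumed scenarios.** The documents give no re-treatment rate and no early-scan rate, so every share below is an assumption. The direction also depends on what 73% and 82% already include.

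*A. If 73%/82% already count every re-treatment as failure*, and the same share m of failures in each arm scores as success, the observed rates are 0.73 + 0.27m and 0.82 + 0.18m.

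| m | Rates | Difference (points) | Power |
|---|---|---|---|
| 5% | 74.35 / 82.9 | 8.55 | 75.9% |
| 10% | 75.7 / 83.8 | 8.1 | 73.0% |
| 20% | 78.4 / 85.6 | 7.2 | 66.7% |
| 30% | 81.1 / 87.4 | 6.3 | 59.7% |

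*B. If 73%/82% are the rates under the SAP rule as written*, any misclassification is already inside them and power stays at 78.6%. Recoding a share r of successes as failures gives rates 0.73(1−r) and 0.82(1−r), with r allowed to differ by arm.

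| r, control / larger coil | Rates | Difference (points) | Power |
|---|---|---|---|
| 1% / 1% | 72.27 / 81.18 | 8.91 | 76.8% |
| 3% / 3% | 70.81 / 79.54 | 8.73 | 73.2% |
| 5% / 5% | 69.35 / 77.9 | 8.55 | 69.7% |
| 3% / 1% | 70.81 / 81.18 | 10.37 | 87.4% |
| 5% / 2% | 69.35 / 80.36 | 11.01 | 90.1% |
| 1% / 3% | 72.27 / 79.54 | 7.27 | 58.2% |
| 2% / 4% | 71.54 / 78.72 | 7.18 | 56.3% |

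In patients, expected successes are 325 × 0.73 = 237.25 and 325 × 0.82 = 266.5. The 3%/1% row therefore recodes about 7 and 3 patients, and the 2%/4% row about 5 and 11.

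*C. Early scans.* If 73%/82% exclude early-scan failures, and an early scan fixes failure in 1%, 5% or 10% of would-be successes in both arms, power is 76.8%, 69.7% or 61.4%.

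**Step 4. Which premise applies?** SAP 6.5.2 ties 73%/82% to the SAP endpoint. Protocol 9.1 attaches the same two percentages to a change in Raymond grade. Neither mentions re-treatment, so the documents do not settle it.

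**The case against.** The strongest reply is that the rule already does most of the work. A re-treatment preceded by a counted Raymond score above 2 is a permanent failure, and re-treatment is compared between arms as a secondary endpoint. Both points stand. A reader might infer that re-treatment escapes the primary endpoint altogether or goes unreported; the documents do not support either.

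Second, what remains is chiefly Raymond 2 remnants, which SAP 5.1 calls adequate. Scoring those patients as failures lets an unblinded decision override the blinded core lab. This is a real cost and a reason to report the core-lab-only result as well. It does not justify crediting the second treatment to the first.

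Third, an unreadable or missing scan is a data-collection failure, since protocol 5.1.2 and 6.2.1 call for image upload. That is fair, but SAP 6.5.3 itself foresees missed and unreadable 12-18 month scans, so the scoring should not depend on perfect capture.

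Fourth, a reader might infer a definite loss of power, or a bias that hides a benefit of larger coils. Neither is supported. The shares are invented, and under scenario B recoding moves power in either direction.

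Fifth, a reader might conclude that early clinically driven scans should be removed from the primary rule. That would discard documented early failures: a patient with Raymond 3 at two months and no later scan would move from failure to imputation. Nor does the protocol's wider definition of success, "Angiographic occlusion, improvement or no change in the post-coiling appearance of the aneurysm as judged by an independent core lab", decide the matter. Its difference from SAP 5.1 is a separate point.

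**Conclusion.** The gap is real but narrow. It covers only patients re-treated before the 12-18 month reading with no counted Raymond score above 2. For them the plan records a success, or imputes the outcome as though no second treatment had occurred, and neither measures durability of the assigned coils. This follows from the text alone.

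The size is unknown, and so is the direction of any effect on the treatment difference or on power. The figures under working are illustrations; they show that a handful of patients per arm, split unequally, can matter in a design with 78.6% power.

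The missing earliest date for clinically driven scans is also real, but changing the primary rule there is a trade-off. A sensitivity analysis is the proportionate response.

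**What to change.** The SAP's statement of purpose allows revision until data lock. Before then:

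1. In SAP 5.1, count any re-treatment of the target aneurysm before the 12-18 month reading as failure, whether or not a score above 2 was recorded.
2. In SAP 6.5.3, apply the same rule when the final scan is missing, so that these patients are failures and are not imputed.
3. Report the present core-lab-only rule as a sensitivity analysis.
4. Add a sensitivity analysis that excludes clinically driven scans taken before the 3-6 month window, leaving the primary rule on such scans unchanged.

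The cost is SAP wording and two further analyses of data already collected. The downside is that some Raymond 2 remnants become failures on an unblinded decision. Item 3 shows how much that matters. If a second stage planned before the index procedure is to be exempt, the plan must say how that intention is documented: protocol 4.2 records planned use of assist devices, but no listed data item records planned staging.
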